1.4 Synopsis

Name of Sponsor/Company: STEBA Biotech S.A.	Protocol	For National Authority Use Only
Name of Finished Product: TOOKAD® Soluble	No: CLIN1601 PCM204	
Name of Active Ingredient: Padeliporfin/ Palladium Bacteriopheophorbide Monolysotaurine (WST11)	Volume:	
TITLE OF STUDY:		
Study of the Efficacy, Safety and Quality of Life after TOOKAD® Soluble Vascular Targeted Photodynamic therapy (VTP) for Minimally Invasive Treatment of Localized Intermediate Risk Prostate Cancer.		
STUDY CENTRE(S):		
It is expected to involve one single center (Memorial Sloan-Kettering Cancer Center) in the United States of America.		
DEVELOPMENT PHASE: This study is designed as a Phase IIb study		
STUDY RATIONALE		
Based on the positive phase II and phase III studies conducted in the United States, Europe, Canada and Latin America, it is expected that TOOKAD® Soluble VTP treatment as a partial gland ablation modality indicated for localized prostate cancer will result in a significant percentage of patients becoming cancer-free, with minimal change from baseline erectile and urinary function and with a good safety profile. These findings have thus far been consistent across the trials in low volume Gleason 3+3 prostate cancer, a disease considered to be low-risk. Among trial participants in the recently completed Phase III Latin American study (PCM304), where few patients with intermediate-risk Gleason score 3+4 cancer were treated, the results appear similar to those of treated men with Gleason 3+3 disease. Therefore, establishing the safety and efficacy of this procedure specifically in men with localized, intermediate risk prostate cancer is an important research objective to be addressed in this study. Interest in performing this study in the U.S. at a center of excellence will provide rigorous evaluation of the technique and oncologic outcomes as well as detailed study of functional metrics.		
STUDY HYPOTHESIS		

TOOKAD® Soluble Vascular Targeted Photodynamic therapy (VTP), as a partial gland ablation therapy for men with unilateral intermediate risk prostate cancer, will result in the absence of detectable, clinically significant prostate cancer in over 70% of treated men.

PRIMARY OBJECTIVE

To evaluate the absence of biopsy detectable Gleason grade 4 or 5 prostate cancer tumors anywhere in the prostate gland on 12-month, post-treatment biopsy following TOOKAD® Soluble-VTP in men with Gleason score 7 (3+4) prostate cancer.

SECONDARY OBJECTIVES

1. To describe the rate of responders, with response defined as the absence of any Gleason grade 4 or 5 biopsy on or before months 24, 36, 48 and 60. If a subject is retreated following a positive biopsy at 3 months and subsequent biopsy shows absence of gleason grade 4 or 5, the subject will be considered to have responded;
2. To describe the rate of responders, with response defined as the absence of any prostate cancer on biopsy on or before months 3, 12, 24, 36, 48 and 60. If a subject is retreated following a positive biopsy at 3 months and subsequent biopsy shows absence of any cancer, the subject will be considered to have responded;
3. To describe the rate of responders, with response defined as the absence of any Gleason grade 4 or 5 biopsy on or before months 12, 24, 36, 48 and 60 in the treated lobe. If a subject is retreated following a positive biopsy at 3 months and subsequent biopsy shows absence of gleason grade 4 or 5, the subject will be considered to have responded;
4. To describe the rate of responders, with response defined as the absence of any prostate cancer on biopsy on or before months 3, 12, 24, 36, 48 and 60 in the treated lobe. If a subject is retreated following a positive biopsy at 3 months and subsequent biopsy shows absence of any cancer, the subject will be considered to have responded;
5. To describe the change in biopsy results between 3 , 12, 24, 36, 48 and 60 months TOOKAD® Soluble-VTP;
6. To describe changes in urinary and erectile function and the potential impact on QOL using International Prostate Symptom Score (IPSS) and International Index of Erectile Function (IIEF) questionnaires up to 60 months;
7. To describe the occurrence of adverse events of TOOKAD® Soluble -VTP treatment in patients with localized prostate cancer;
8. To describe the occurrence of severe prostate cancer-related events: cancer extension to T3, metastasis and prostate cancer-related death;
9. To document the use of secondary prostate cancer therapies following TOOKAD® Soluble-VTP;
10. To describe the change in PSA from blood samples following TOOKAD® Soluble- VTP.

METHODOLOGY – STUDY DESIGN

This is a single center, single-arm, open-label, 60-month follow-up phase IIb clinical trial. Men with localized prostate cancer will receive TOOKAD® Soluble VTP under general anesthesia. Prior to the TOOKAD® Soluble VTP, patients will undergo routine ultrasound examination in the operating room for morphometric description of the prostate and to facilitate accurate treatment guidance for the treatment with TOOKAD® Soluble VTP. Treatment will then be applied to the prostate gland as a hemiablation procedure designed to destroy the lobe of the prostate gland that contains the Gleason score 7 (3+4) cancer. Afterwards, patients will be followed for 5 years (60 months) with clinical evaluation, questionnaires on QOL, erectile and urinary functions, and PSA testing. In addition, treatment outcomes will be assessed based on prostate biopsy results at 3, 12, 24, 36, 48 and 60 months after the TOOKAD® Soluble treatment. All patients will undergo biopsy at 3 and 12 months. Thereafter, biopsy will be performed for cause per institutional standards. If the Month 3 biopsy is positive for any cancer, patients will be allowed a single re-treatment by TOOKAD® Soluble VTP to one or both lobes. However, patients with evidence of clinical deterioration on the same side such as worsening Gleason score, increased core involvement with cancer tumor grades on the 3-month biopsy and/or rising PSA will be withdrawn from the study and proceed with standard care. In addition, patients who experience treatment related Grade 3-4 adverse events during their first treatment will not be re-treated at month 3 and will be proceed with standard care if the month-3 biopsy contains cancer, on the same or contralateral side.

This study is a phase IIb trial using optimal dose of TOOKAD® Soluble and optimal light-energy level conditions that were determined in previous phase I and II studies and confirmed by the phase III studies among patients with localized prostate cancer. Partial gland ablation therapy using thermal approaches, as an alternative to radical treatments for low-volume prostate cancer, is a treatment option currently being offered to men with prostate cancer in the U.S. as a tailored means to manage their disease with fewer side effects. Previous studies of TOOKAD® Soluble treatment have suggested that this non-thermal approach is an effective therapeutic strategy to achieve ablation of the prostatic tissue that contains the cancer lesion in this patient population. Considering the available clinical data, a phase IIb is considered appropriate at this stage, with the main aim of confirming, in intermediate risk patients, previous findings in low and favorable intermediate risk prostate cancer patients. Moreover, a single center design was also considered appropriate, as it allows for optimal standardization of the technique and better control over data acquisition.

NUMBER OF PATIENTS:

In order to obtain at least 44 evaluable patients, a total of 50 patients will be included and will be treated with TOOKAD® Soluble VTP in this study.

DRUG DESCRIPTION AND PREPARATION:

TOOKAD® Soluble - padeliporfin di-potassium (WST11) Drug Product is a dark coloured powder for solution for injection. It is packaged in amber glass vials. It is manufactured in two different presentations:

- 200 mg TOOKAD® Soluble in a 30 mL vial with blue flip-off cap, to be reconstituted, just before administration, with 20 mL of 5% dextrose solution for injection
- 400 mg TOOKAD® Soluble in a 50 mL vial with white flip-off cap, to be reconstituted, just before administration, with 40 mL of 5% dextrose solution for injection

The two presentations have the same formulation which is produced in exactly the same process and they differ only in the amount of TOOKAD® Soluble per vial, the size of the vial and the colour of the flip-off cap.

For both presentations the final concentration of TOOKAD® Soluble solution to be injected is 10 mg/mL.

INCLUSION CRITERIA:

Subjects will be eligible for inclusion in the study if all of the following criteria are met:

1. Men over 18 years of age.
2. Patients who have had a multiparametric MRI of the prostate performed and have undergone transrectal systematic biopsy plus biopsy of any volumes considered suspicious per the MRI (PIRADS version 2 score of 4 or 5) within 6 months before signing consent.
3. Histologic diagnosis of prostate cancer identifying Gleason score of 3+4 on one half of the prostate gland in no more than 2 sextants of the prostate gland and not present in more than 50% of any one core taken systematically. The involvement criterion does not apply to cores taken from MRI suspicious volumes.
4. Patients with concomitant Gleason score 3+3 prostate cancer in less than 50% of any core at any site will be considered eligible.
5. Prostate cancer stage up to cT2a – N0/Nx – M0/Mx.
6. Prostate volume ≥ 25 mL and ≤ 70 mL.
7. Serum PSA ≤ 10 ng/mL.

8. Men who are sexually active with women of childbearing potential must use contraceptive method with a failure rate of less than 1% per year. Contraception should be continued for a period of 90 days after the VTP procedure. The individual methods of contraception may be determined in consultation with the investigator.
9. Signed Informed Consent Form.

GENERAL EXCLUSION CRITERIA :

Subjects will not be eligible for the study if meeting any of the following criteria:

1. Unwillingness to accept the treatment;
2. Any prior or current treatment for prostate cancer, including surgery, radiation therapy (external or brachytherapy) or chemotherapy;
3. Any surgical intervention for benign prostatic hypertrophy;
4. Any condition or history of illness or surgery that might pose an additional risk to men undergoing the VTP procedure;
5. Life expectancy less than 10 years;
6. Participation in another clinical study involving an investigational product within 1 month before study entry;
7. Inability to understand the informed consent document, to give consent voluntarily or to complete the study tasks, especially inability to understand and fulfill the health-related QOL questionnaire;
8. Subjects in custody and or residing in a nursing home or rehabilitation facility;
9. Biopsy proven locally advanced or metastatic prostate cancer.

SURGERY AND OTHER TREATMENT-RELATED CONDITIONS OF EXCLUSION

Any condition or history of illness or surgery that may pose an additional risk to men undergoing the VTP procedure such as:

1. Any condition or history of illness or surgery that in the opinion of the investigator might affect the conduct and results of the study or pose additional risks to the subject (e.g., cardiac or respiratory disease precluding general anesthesia; anticoagulant treatment which cannot be temporarily withdrawn for the procedure).
2. Medical conditions that preclude the use of general anesthesia;
3. Any condition or history of active rectal inflammatory bowel disease or other factors which might increase the risk of fistula formation;

4. Hormonal manipulation (excluding 5-alpha-reductase inhibitors) that alters androgen production within the previous 6 months;
5. History of urethral stricture disease;
6. History of acute urinary retention within 6 months of study entry;
7. Anticoagulant drugs (e.g., warfarin) that could not be withdrawn during the 10 days prior to the VTP procedure or antiplatelet drugs (e.g. aspirin) that could not be withdrawn during the 10 days prior to the VTP procedure and 3 days after VTP;
8. Renal and hepatic disorders with values of >1.5 times the upper limit of normal (ULN) or blood disorders (upon clinician judgment);
9. A history of sun hypersensitivity or photosensitive dermatitis.

TREATMENT CONDITIONS

Subjects will fast per institutional standards before the VTP procedure in preparation for the use of anesthesia as per institutional standards. TOOKAD® Soluble VTP consists of the combination of a single, 10-minute IV infusion of TOOKAD® Soluble at the dose of 4 mg/kg, followed by the illumination of the zone to be treated with a 753-nm laser light delivered through transperineal interstitial optical fibers at a power of 150 mW/cm and light energy of 200 J/cm applied over 22 minutes and 15 seconds. Treatment for an individual patient is guided by the software TOOGUIDE TRUS, which is operated by the urologist and allows for the acquisition of TRUS images while the patient is in the treatment position, thus defining the prostate contours, the target and the optimal fiber configuration to maximize light dose in the target while sparing the surrounding tissues by allowing for a margin of at least 5 mm between the light delivery fibers and the rectal wall, the apex of the prostate, and the urethra. Fibers are then introduced into transparent catheters and positioned in the prostate areas of interest using a transperineal template. In case of unilateral disease, treatment of one lobe is applied. In case of bilateral disease, bilateral treatment is applied simultaneously or sequentially at the surgeon's discretion.

Re-treatment of lobes found positive for cancer at 3 months of follow-up is allowed. Re-treatment will be performed using the same drug and light dosing parameters as described for initial treatment and applied in the same manner. Re-treatment will be allowed 2-4 months following 3 month biopsy. Re-treatment may include either one (hemi gland) or both lobes (whole gland) of the prostate. As mentioned above, in case of signs of cancer progression on the same side or in case of treatment-related Grade 3-4 adverse events during their first treatment, patients will not be retreated and will be withdrawn and managed as per local standard of care, unless justification for continuing on study is specifically sought and approved from the IRB.

DURATION OF STUDY:

Patients will be followed until 60 months with assessment of the primary end-point at 12 month, and patients' questionnaires at 1, 3, 6 and 12 months and every 12 months until 60 months.

DURATION OF TREATMENT and STUDY PROCEDURES:

The VTP procedure can be planned, following surgeon's advice, as a day-case surgery. Patients will be hospitalized in the morning of the day of the procedure. The procedure is done in the operating room under general anesthesia. The total duration of the procedure is about 1 ½ to 2 hours (including anesthesia, fiber placement and illumination with the laser light). This includes a 10 minutes infusion of TOOKAD® Soluble, followed immediately by light delivery over approximately 22 minutes.

After treatment the subject will recover under routine postoperative monitoring in a dimmed room for at least 6 hours and will be discharged on the day of the procedure following this interval, unless the investigator feels that the patient should be hospitalized longer for medical reasons. Urinary catheter will be kept at least 6h after the VTP procedure.

CRITERIA FOR EVALUATION:**Primary endpoints**

- Binary response to treatment defined as absence of Gleason grade 4 or 5 on biopsy at month 12.

Secondary endpoints

- Binary response to treatment defined as the absence of any Gleason grade 4 or 5 biopsy on or before months 24, 36, 48 and 60. If a subject is retreated following a positive biopsy at 3 months and subsequent biopsy shows absence of gleason grade 4 or 5, the subject will be considered to have responded;
- Binary response to treatment defined as the absence of any prostate cancer on biopsy on or before months 3, 12, 24, 36 and 60. If a subject is retreated following a positive biopsy at 3 months and subsequent biopsy shows absence of any cancer, the subject will be considered to have responded;
- Binary response to treatment defined as the absence of any Gleason grade 4 or 5 biopsy on or before months 12, 24, 36, 48 and 60 in the treated lobe. If a subject is retreated following a positive biopsy at 3 months and subsequent biopsy shows absence of gleason grade 4 or 5, the subject will be considered to have responded;
- Binary response to treatment defined as the absence of any prostate cancer on biopsy on or before months 3, 12, 24, 36, 48 and 60 in the treated lobe. If a subject is retreated following

a positive biopsy at 3 months and subsequent biopsy shows absence of any cancer, the subject will be considered to have responded;

- Changes in biopsy result between 3, 12, 24, 36, 48 and 60 months after the procedure.
- Patients' reported outcome measures (PROMs) impairment: urinary symptoms using IPSS and erectile functions using IIEF prior to treatment beginning and then 1, 3, 6, 12, 24, 36, 48 and 60 months after completing treatment
- Severe prostate cancer-related events: cancer extension to T3, metastasis or prostate cancer-related death
- Use of secondary prostate cancer treatment following VTP will include surgical removal of the prostate gland, radiation treatment to the prostate gland, use of hormone or chemotherapies.
- Adverse events
- Serum PSA measurements in ng/mL.

SAMPLE SIZE JUSTIFICATION

A proportion of responders of $r=70\%$ at 12 months is considered to be a clinically significant expectation in localized intermediate-risk prostate cancer patients.

Based on historical data in similar series of patients, a minimum of $N=44$ patients is required to test the null hypothesis $H_0: "r \leq 70\%"$ vs. $H_1: "r > 70\%"$, with 80% power and 5% as alpha risk.

MANUFACTURING INVESTIGATIONAL PRODUCT:

TOOKAD® Soluble is manufactured by Praxis Pharmaceutical S.A, Vitoria-Gasteiz, Spain.

TOOKAD® Soluble batches are released by Steba Laboratories, Ness Zion, Israel.

Laser equipment: Intermedic Arfran S.A, Spain

FLOW CHART: Schedule of Events

Procedure	V1 and screening period	V2 VTP	V3 Day 7+/- 2 days	V4 Month 1 +/- 1 wk	V5 Month 3 +/- 2 wks	V6 Month 6 +/- 2 mos	V7 Month 12 +/- 2 mos	V8-11 Annual f/u +/- 3 mos
Informed Consent	X							
Inclusion/exclusion Criteria	X							
Medical History	X							
TNM Staging	X							
VTP Treatment		X						
Clinical Examination	X	X ^a						
Prostate Biopsy	X ^b ≤6mos before consent				X ^c		X	X ^d
Digital Rectal Examination	X							
Prostate Specific Antigen	X ^e	X		X	X	X	X	X
Standard Hematologic Tests	X ^e	X ^a		X	X	X	X	X
Standard Blood Chemistry Tests	X ^e	X ^a		X	X	X	X	X
Standard Blood Coagulation Tests	X ^e							
Additional Inclusion Blood Tests	X ^e							
Prostate Volume	X	X						
MRI	X ^d				X		X	X ^d
Patient-Reported Outcome Measures (PROMs)	X			X	X	X	X	X
Study Medication		X						
Concomitant Medications	X	X ^a	X	X	X	X	X	X
Adverse Events		X ^a	X	X	X	X	X	X

^a Before and after VTP procedure^b In case of unilateral disease, focal treatment of one lobe will be applied. In case of bilateral disease (discovered at entry or during follow-up), bilateral treatment will be applied consecutively or simultaneously.^c Visit at 3 months (± 2 weeks). Retreatment of lobes found positive for cancer will be allowed 2-4 months following positive biopsy, except in case of cancer progression on the same side or grade 3-4 related AE during the first treatment unless justification for continuing on study is specifically sought and approved from the IRB.^d As performed per standard of care^e Obtained at V1 or available in the patient file if < 4 weeks before V1

GLOSSARY OF ABBREVIATIONS

Abbreviation	Definition
5-ARI	5-Alpha Reductase Inhibitor
AE	Adverse Event
ALT	Alanine Aminotransferase
AMD	Age-related Macular Degeneration
APTT	Activated Partial Thromboplastin Time
AS	Active Surveillance
AST	Aspartate Aminotransferase
CBC	Complete Blood Count
COMP	Comprehensive Metabolic Panel
CRF	Case Report Form
CRO	Contract Research Organisation
CTCAE	Common Terminology Criteria for Adverse Events
DLI	Drug-Light Interval (the interval between start of infusion and start of illumination)
DRE	Digital Rectal Examination
DSMB	Data and Safety Monitoring Board
eCRF	Electronic Case Report Form
EDC	Electronic Data Capture
EMA	European Medicines Agency
EPIC	Expanded Prostate Cancer Index Composite
F(VOA)	Focal Vascular Occluding Agent
GCP	Good Clinical Practice
ICH	International Conference on Harmonization
IEC	Independent Ethics Committee
IRB	Institutional Review Board
IV	Intravenous

LDI	Light Density Index
MedDRA	Medical Dictionary for Regulatory Activities
MRI	Magnetic Resonance Imaging
NCI	National Cancer Institute
NOAEL	No Observed Adverse Effect Level
PDT	Photodynamic Therapy
PICF	Patient Informed Consent Form
PROMs	Patient Reported Outcome Measures
PSA	Prostate Specific Antigen
PTT	Partial Thromboplastin Time
QoL	Quality of Life
ROS	Reactive Oxygen Species
RP	Radical Prostatectomy
SAE	Serious Adverse Event
SAS	Stastitical Analysis System
SOC	System Organ Class
SOP	Standard Operating Procedure
TG	Treatment Guidance
TRUS	TransRectal Ultrasound
TURP	TransUrethral Resection of the Prostate
US	UltraSound
VEGF	Vascular Endothelial Growth Factor
VTP	Vascular-Targeted Photodynamic therapy
WHO	World Health Organisation

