3.2 Primary objective

- To evaluate for the absence of biopsy detectable Gleason grade 4 or 5 prostate cancer on 12-month, post-treatment biopsy following TOOKAD® Soluble- VTP in men with Gleason score 7 (3+4) prostate cancer.

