6.4.5 Visit 5 (V5): Month 3 (±2 weeks)

The procedures for this assessment are:

1. Multiparametric MRI of the prostate with contrast. The procedure for this MRI is described in Appendix 2
2. Blood collection for laboratory and PSA testing
3. Performance of prostate biopsy
4. Recording of AEs
5. Assessment of concomitant medication
6. Collection of IPSS and IIEF questionnaires

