6.4.7 Visit 7 (V7): Month 12 (±2 months)

The procedures for this visit are:

1. Blood collection for laboratory and PSA testing
2. Recording of AEs
3. Assessment of concomitant medication
4. Collection of IPSS and IIEF questionnaires
5. Performance of prostate biopsy

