6.4.10 Additional Visits

A single re-treatment of lobes found positive for cancer at 3-months follow-up is allowed.

Those additional treatments will be performed in the same conditions as for the first VTP procedure (section 6.4.2.). The schedule of visits will remain unchanged and the whole study duration will be sixty months.

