### **Primary efficacy analysis**

The proportion of patients with no pattern 4 or 5 found in the 12 month biopsy will be reported along with a one-sided 90% confidence interval. Patients who have pattern 4 or 5 found before 12 months and who receive radical therapy will be treated as treatment failures. The treatment will be considered a success if the lower bound, rounded to 0.01, is 70% or higher. For a sample size of 44, this means that treatment will be declared a success if 35 or more patients respond.

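### A re-treated man's Month 12 biopsy falls 2.5 to 9.5 months after his last VTP, and the SAP does not settle how he counts in the primary analysis

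*Protocol*

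**What the plan says.** **Timing.** The treatment conditions in the Protocol synopsis (1.4) state: "Re-treatment will be allowed 2-4 months following 3 month biopsy". Footnote c of the flow chart uses the same anchor: "Retreatment of lobes found positive for cancer will be allowed 2-4 months following positive biopsy". On what happens to the calendar afterwards, Protocol 6.4.10 says: "The schedule of visits will remain unchanged and the whole study duration will be sixty months". The Month 3 visit has a window of two weeks either side (6.4.5) and the Month 12 visit a window of two months either side (6.4.7). Biopsy is required of everyone only at these two visits. After Month 12 it is left to the investigator and standard of care (7.1).

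**Endpoint.** The primary objective (Protocol 3.2) refers to a "12-month, post-treatment biopsy following TOOKAD® Soluble- VTP". Protocol 10.3 and the SAP's primary endpoint make the Month 12 result the primary variable and do not mention re-treatment. The secondary endpoints (Protocol 10.4.1) do: a re-treated man whose later biopsy is clear counts as a responder.

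**Analysis.** The SAP's primary efficacy analysis reads: "The proportion of patients with no pattern 4 or 5 found in the 12 month biopsy will be reported". It also counts as failures the men with pattern 4 or 5 before Month 12 who go on to radical therapy, and says nothing of those who go on to a second VTP. The SAP's efficacy population is defined without reference to re-treatment. Its efficacy analysis paragraph applies that population to all analyses and adds a secondary analysis that includes men re-treated at 3 months.

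**The concern.** The objective reads as if every man is biopsied about a year after treatment. For a man treated twice, the visit clock starts at the first session while the treatment that his biopsy evaluates may be the second. Two questions follow.

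- How far from 12 months is his primary biopsy?
- Does his result enter the primary proportion, and if so as what kind of response?

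What is at stake is the claim that the trial can make at Month 12. The SAP's pass mark is 35 responders of 44, so 34 fails and 35 passes. The handling of a few men can decide the result and should be fixed before it is known.

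**Working it through.** The documents state no interval from re-treatment to the primary biopsy, so there is no figure to reproduce. The interval follows from the windows.

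**Inputs.** Month 3 biopsy ± 2 weeks (Protocol 6.4.5); re-treatment 2 to 4 months after it (synopsis and footnote c); Month 12 biopsy ± 2 months (6.4.7); schedule not reset (6.4.10). Two weeks = 14 / 30.4375 = 0.46 month.

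**Date of second VTP**, in months from first VTP:
- earliest: 3 − 0.46 + 2 = 4.54
- latest: 3 + 0.46 + 4 = 7.46

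**Interval from last VTP to Month 12 biopsy** = biopsy date − date of last VTP:

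| | Shortest (months) | Longest (months) |
|---|---|---|
| Treated once | 12 − 2 = 10 | 12 + 2 = 14 |
| Re-treated, limits of the windows | 10 − 7.46 = 2.54 (about 77 days) | 14 − 4.54 = 9.46 |
| Re-treated, nominal visit dates | 12 − 7 = 5 | 12 − 5 = 7 |

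The two groups do not overlap: no permitted combination of dates gives a re-treated man even 10 months. Because Month 12 is the last mandatory biopsy, the protocol never guarantees him one at 10 months or more after his last session.

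**How he counts.** Setting the analysis texts side by side gives two readings.

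1. *Included.* The efficacy population does not exclude him, Protocol 10.3 makes no exception, and the failure rule covers radical therapy only. The primary proportion then mixes single-session responses at 10 to 14 months with two-session responses at 2.5 to 9.5 months.
2. *Excluded.* The secondary analysis that includes re-treated men implies that the main one does not. Men with cancer at Month 3 then leave the denominator, which raises the rate if they would have responded less often than the rest. It also uses up evaluable patients: 50 are planned to obtain 44, a margin of 50 − 44 = 6 for all losses together.

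**Illustration for the first reading, by assumption only.** Take a true rate of 70%, a fraction f re-treated, and a lift d in their observed success rate from the shorter interval. The observed rate is 0.70 + f × d, and the chance of declaring success is P(X ≥ 35) for a binomial with n = 44.

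| f | d | Observed rate | Chance of success |
|---|---|---|---|
| none | none | 0.700 | 10.9% |
| 5% | 10 points | 0.705 | 12.3% |
| 20% | 20 points | 0.740 | 25.8% |
| 30% | 30 points | 0.790 | 55.2% |

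The documents give neither f nor d. The table shows that the effect could be anywhere from negligible to large; it does not estimate it.

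**The case against.** The strongest case for the plan has four parts.

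*The SAP may already keep re-treated men out of the primary result.* A reader might infer that the primary proportion pools both groups and is therefore inflated. The documents do not establish this: the efficacy analysis paragraph can fairly be read the other way. What stands is that the two SAP paragraphs point in different directions, and that exclusion raises a selection problem of its own.

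*The shortest interval is a corner case.* It needs a late Month 3 biopsy, re-treatment at the full four months and an early Month 12 biopsy in the same man. This is right, and 5 to 7 months is the fairer typical figure. The largest phase II study cited in Protocol 2.2.4 itself reported biopsy at 6 months. Even so, 5 to 7 months is about half of what the objective names.

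*Re-treatment does not always mean that the first session failed.* A reader might treat every re-treated man as a treatment failure in disguise. The protocol does not support that. Re-treatment covers any cancer in either lobe, including 3+3 disease in a lobe not treated before, and men with same-side deterioration are withdrawn instead. Some overlap with the primary endpoint remains, because the withdrawal criteria in 5.5.4 appear to leave room to re-treat men with limited grade 4.

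*A fixed landmark with one re-treatment allowed is a legitimate strategy.* Agreed, and 6.4.10 shows that it was deliberate. The SAP also reports the number re-treated and analyses Month 3 separately. But the objective does not describe that strategy, and none of these tables shows the Month 12 result by re-treatment status or by time since last VTP.

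Finally, nothing in the documents says how long residual grade 4 or 5 takes to become detectable, so an upward bias is a plausible expectation and not a finding.

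**Conclusion.** The point holds as a mismatch between the stated endpoint and the calendar, together with an unsettled analysis rule. For every re-treated man the primary biopsy comes 2.5 to 9.5 months after his last VTP, against 10 to 14 months for the others. This rests only on the protocol's own windows. It does not show that the trial's success rate will be inflated: that would need the share re-treated, the reason for re-treatment, the effect of the shorter interval and a settled reading of the SAP, none of which the documents supply. Under either reading, the result cannot be described as absence of grade 4 or 5 at 12 months after treatment for all men.

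**What to change.** 1. Reconcile Protocol 3.2, 6.4.10 and 10.3 with the SAP's efficacy population, efficacy analysis and primary efficacy analysis. The SAP should state that re-treated men stay in the primary denominator and that Month 12 is counted from the first VTP.
2. In the SAP, derive the interval from last VTP to the Month 12 biopsy and show the primary proportion by re-treated yes/no. Add a sensitivity analysis that counts men re-treated after grade 4 or 5 at Month 3 as failures, which gives the single-session response.
3. Word the conclusion as response at Month 12 after first VTP, with one re-treatment allowed.

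No change to the timing of biopsy or re-treatment is proposed. The cost is one derived variable, one extra table and a slightly narrower claim. If the rule is written before the Month 12 results are reviewed, it also removes any suspicion that the denominator was chosen afterwards.
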